### **13. STATISTICS**

Analysis of the clinical efficacy data will consist of modeling endpoints, including PD, CAL, BOP, and FMPI, with treatment group as the main effect and adjusted for baseline. Post-baseline treatment comparisons will be modeled through a generalized estimating equations (GEE) method (with a linear link and exchangeable covariance matrix), adjusting for the baseline value. Methods of analysis for periodontal microbial flora profiles, inflammatory cytokine levels in GCF and in serum and RBL will be described in separate statistical analyses plans. Results will be considered significant if  $p < 0.05$ .

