3. GENERAL ANALYSIS AND REPORTING CONVENTIONS

For continuous endpoints, the summary statistics will generally include number of subjects with data (n), mean, standard deviation, median, minimum and maximum. No preliminary rounding will be performed; rounding will only occur after analysis. To round, the digit to right of last significant digit will be considered: if < 5 then round down, if ≥ 5 then round up. Means and medians will be presented with one more decimal place than the precision of the data. Standard deviations will be presented with two more decimal places than the precision of the data. Percentages will be presented with one decimal place. Minimums and maximums will be presented with the same precision as the original data.

For categorical endpoints, the summary statistics will generally include: number of subjects randomized and/or dosed, number of subjects with data, and the percentage of those with data in each category. Frequency distributions will be presented as appropriate.

Analysis of the clinical efficacy data will consist of modeling endpoints, including change from baseline in PD, CAL, BOP, and FMPI, with treatment group, patients, smoking status, and investigational site as main effects and adjusting for baseline values of a given endpoint. Post-baseline treatment comparisons will be modeled through a GEE method (with a linear link and exchangeable covariance matrix), adjusting for the baseline value. Methods of analysis for periodontal flora, inflammatory cytokine levels in GCF and in serum, and RBL will be described in separate statistical analysis plans.

Hypothesis testing, unless otherwise indicated, will be two-sided. When confidence intervals are presented, they will be two-sided with a confidence coefficient of 95%. Actual P-values will be reported to 3 decimal places if greater than 0.001. If less than 0.001, the value ' <0.001 ' will be reported.

The statistical software, SAS[®] version 9.3 or above, will be used for all summaries and statistical analyses.

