8.3.2 Secondary Efficacy Analyses

Additional secondary efficacy analyses will be performed to test the effects of treatment group and their interactions on the secondary endpoints of the change from baseline in CAL and BOP at Day 270. For the CAL analysis, the GEE analyses will be performed with the same statistical model as described in the primary PD efficacy analysis but with the change from baseline in CAL of tooth-sites with baseline PD ≥ 6 mm as the dependent

variable. Separate hypotheses will be performed for testing the treatment effects of group 1 versus group 3 (placebo) and group 2 versus group 3 (placebo). As described above, this model will include the baseline smoker status (smoker or non-smoker) by treatment group interaction. For the secondary efficacy analyses of the BOP change from baseline, ANCOVA will be performed with treatment group as the main effect, and covariates for baseline PD, site, patients, smoker status, and the baseline smoker status (smoker or non-smoker) by treatment group interaction. Point estimates and 95% confidence intervals will be presented for the treatment group differences in CAL and BOP change from baseline at Day 270 and by baseline smoker status.

The CAL and BOP secondary analyses described above will be tested hierarchically in the order of: CAL change from baseline at Day 270, and BOP (presented as a whole mouth average percentage) change from baseline at Day 270. The treatment effects for the CAL or BOP change from baseline at the Day 270 Visit will be compared between Treatment Group 1 and Placebo, and between Treatment Group 2 and Placebo. The alpha will be set at 0.025 to allow for the Bonferroni correction for 2 multiple comparisons for secondary endpoints. Since the smoker status by treatment group interaction is acting as a gatekeeper for further inference testing by smoker status, no additional corrections will be made for multiplicity for any additional analyses of the effects of treatment on CAL and BOP by smoker status. These analyses will be performed once all the subjects (excluding those withdrawn) completed their 270-Day Visit.

All primary and secondary analyses performed on the ITT population will be repeated using the per protocol population.

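### The smoking-by-treatment interaction, used as a gatekeeper for uncorrected by-smoker tests of CAL and BOP, controls false findings only weakly: it protects when nothing works, but not when one arm or one stratum truly responds

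*SAP*

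**What the plan says.** SAP 8.3.2 puts the smoker-by-treatment interaction in the models for CAL and BOP at Day 270. Each active arm is tested against placebo: "The alpha will be set at 0.025 to allow for the Bonferroni correction for 2 multiple comparisons for secondary endpoints". CAL comes before BOP: "The CAL and BOP secondary analyses described above will be tested hierarchically in the order of: CAL change from baseline at Day 270". The section then adds that "the smoker status by treatment group interaction is acting as a gatekeeper for further inference testing by smoker status", and on that ground "no additional corrections will be made for multiplicity for any additional analyses of the effects of treatment on CAL and BOP by smoker status".

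Four things are not stated:
- the significance level of the interaction test;
- its form (one joint 2-df test, or one test per active arm);
- the level of the by-smoker tests;
- whether a by-smoker test requires a significant overall CAL or BOP comparison.

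Other parts of the SAP are more cautious about smoking. For PD, 8.3.1 plans only point estimates and 95% intervals by smoker status. Section 8.4 treats the further smoking analyses of PD and CAL as exploratory, and the SAP synopsis lists the smoker/treatment interaction for PD and CAL among the exploratory endpoints. Section 8.3.2 itself already plans by-smoker estimates and 95% intervals for CAL and BOP.

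**The concern.** A significant interaction says that the treatment effect differs between smokers and non-smokers. It does not test whether treatment works in either stratum. It therefore cannot stand in for a multiplicity correction of the within-stratum tests, of which there are four per endpoint (two active arms, two strata).

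The weak spot is a real effect confined to one arm or one stratum. That effect makes the interaction significant, and the true-null comparisons that remain are then tested with no correction. This is also the situation in which a by-smoker claim is most likely to be made. At stake is a false statement that ST266 improves CAL or BOP in smokers, or in non-smokers. As written, CAL and BOP by smoker status get looser inference than the primary endpoint does.

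**Working it through.** **The plan's own figure.** SAP 2.6 gives 44 per group for a 0.5 mm difference, SD 0.7 mm, two-sided 0.025 and 85% power. The normal formula n = 2(2.241 + 1.036)² × 0.7² / 0.5² gives 42.1, so 43; the t-test version gives 43.4, so 44. The figure reproduces. It supplies a natural effect size, 0.5/0.7 = 0.71 SD, but the documents give no error rate for the gatekeeper procedure.

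**Inputs from the documents.** Three arms, 50 enrolled per arm, 1:1:1 within smoker strata; two contrasts: "compared between Treatment Group 1 and Placebo, and between Treatment Group 2 and Placebo"; and SAP section 3: "Hypothesis testing, unless otherwise indicated, will be two-sided". The possible by-smoker levels are 0.05 (the Protocol section 13 general threshold) and 0.025 (if the Bonferroni level of 8.3.2 carries over).

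**Assumptions.** Joint 2-df interaction test at 0.05 or 0.10; smokers 20% to 50%; one normally distributed value per subject with common variance.

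**Method.** For arm j, let d_j be the smoker mean minus the non-smoker mean. With n_S smokers and n_N non-smokers per arm and pooled variance s²:
- interaction: F = Σ(d_j − d̄)² / [2s²(1/n_S + 1/n_N)], on 2 and 144 df (150 subjects − 6 cells);
- by-smoker test in stratum k: t = (active mean − placebo mean) / (s√(2/n_k)).

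An error is counted when the interaction is significant and at least one true-null by-smoker test is also significant. Results are by simulation, 300,000 to 1,000,000 trials per setting.

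**No effect anywhere, 20% to 50% smokers, per endpoint**

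| Interaction level | By-smoker level | False finding | Same, among trials with a significant interaction | False finding, no gatekeeper |
|---|---|---|---|---|
| 0.05 | 0.05 | 3.8% to 4.0% | 75% to 80% | 17.2% |
| 0.10 | 0.05 | 6.3% to 6.6% | 63% to 66% | 17.2% |
| 0.05 | 0.025 | 2.7% to 3.0% | 53% to 59% | 9.0% |
| 0.10 | 0.025 | 4.2% to 4.3% | 42% to 44% | 9.0% |

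Check: four independent tests at 0.05 would give 1 − 0.95⁴ = 18.5%. The shared placebo arm brings this to 17.2%.

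**Real effect in one stratum, 30% smokers, interaction at 0.05, per endpoint.** Ranges cover the effect lying in smokers or in non-smokers. The rate without a gatekeeper is in brackets.

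| Who responds | True-null tests left | Interaction significant | False finding, tests at 0.05 | False finding, tests at 0.025 |
|---|---|---|---|---|
| Both arms, 0.71 SD | 2 | 37% | 4.3% to 5.0% (9.1%) | 2.2% to 2.6% (4.6%) |
| One arm, 0.71 SD | 3 | 37% | 7.4% to 7.7% (13.6%) | 4.2% to 4.3% (7.0%) |
| Both arms, 2 SD | 2 | 99.8% | 8.9% to 9.0% (9.1%) | 4.5% to 4.6% (4.6%) |
| One arm, 2 SD | 3 | 99.8% | 13.5% (13.6%) | 6.9% to 7.0% (7.0%) |

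At 0.71 SD the gatekeeper still roughly halves the error. At 2 SD it changes almost nothing.

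**CAL and BOP together, no effect.** If each endpoint has its own interaction test at 0.05 and by-smoker tests at 0.05, the chance of any false by-smoker finding is 5.4% to 7.5% for a CAL-BOP correlation of 0.9 down to 0.

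**The case against.** A reader might infer from the 63% to 80% in the fourth column that the gatekeeper offers little protection at all. The documents do not support that. Those percentages apply only to trials in which the interaction was falsely significant, which happens 5% or 10% of the time. With no effect anywhere the error cannot exceed the level of the interaction test, and the gatekeeper cuts it from about 17% to about 4% or 6.5%. The high percentages also assume by-smoker tests at 0.05. The sentence just before the waiver sets 0.025, and no additional correction can be read as keeping that level; the range is then 42% to 59%.

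Nor does the text settle that CAL and BOP are tested by smoker status independently of each other. The CAL-then-BOP order could be read as covering the by-smoker tests, in which case BOP would add no error when nothing works. The combined 5.4% to 7.5% holds only on the other reading.

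Finally, these are secondary endpoints in a phase 2a trial, PD by smoker status gets no such tests, and the primary conclusion is untouched.

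All of this stands and limits the size of the problem. It does not rescue the SAP's reason for the waiver, because protection when nothing works says nothing about the remaining true-null tests once something does.

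**Conclusion.** The point holds as one of weak control. The interaction test limits false by-smoker findings when treatment has no effect anywhere, but it does not justify dropping correction when one arm or one stratum responds. Per endpoint, with by-smoker tests at 0.05, the error is about 4% to 8% near the planned effect size and 9% to 13.5% for a 2 SD effect. At 0.025 it is about 2% to 4% and 4.6% to 7%. It therefore passes 5% in some settings and not in others: at 0.05 mainly when a single arm responds or the effect is large, and at 0.025 only when a single arm has a large effect.

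The figures depend on the smoker share, the interaction level and form, and the by-smoker level, none of which the SAP gives. They come from a subject-level normal model, not the tooth-site GEE that the SAP plans for CAL. The matter should be put right, but it does not bear on the primary analysis.

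**What to change.** In SAP 8.3.2, delete the sentence that makes the interaction a gatekeeper and waives correction. Keep the by-smoker point estimates and 95% intervals for CAL and BOP that the section already plans, state that no p-values accompany them, and label them exploratory. This matches the estimates-and-intervals presentation of PD by smoker status in 8.3.1 and the exploratory label in 8.4. Report the interaction p-value as descriptive.

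This is a wording change and loses no estimates. Its cost is that no formal by-smoker claim can be made on CAL or BOP.

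If the sponsor wants such a claim, the SAP must instead state the interaction test, its level and the by-smoker level, say how the CAL-BOP order applies, and correct the tests. As an illustration at 30% smokers, Bonferroni over four tests (0.05/4 = 0.0125 each) gives, per endpoint, 1.9% (interaction at 0.05) or 2.6% (at 0.10) with no effect, and 3.5% when one arm has a 2 SD effect in one stratum. The price is lower power within strata.

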8.3.3 Efficacy Analyses at Other Time Points

The same technique used for the primary and secondary endpoints will be used for the other assessed time points. Point estimates and 95% confidence intervals will be presented for change from baseline at each assessment time point. The p-values will not be presented for these analyses. Actual value and change from baseline will be presented for each scheduled collection visit for the summarized endpoint. Please refer to Section 15.2 for the schedule of assessments.

8.3.4 Exploratory Efficacy Analyses

FMPI will be analyzed using the GEE method described in section 8.3.1 at days 90, 180, and 270. Additionally, CAL change from baseline at days 180 and 270 using all tooth-sites will be analyzed using GEE. PD change from baseline at days 90, 180, and 270 using a whole-mouth average will be analyzed using ANCOVA with the model described previously.

Analysis methods for the exploratory efficacy outcomes, (1) inflammatory cytokines in GCF and serum, (2) microbial periodontal flora and (3) RBL will be described in a separate statistical analysis plan.

8.4 Examination of Subgroups

To explore the potential effect of age and gender on response, and to further explore the effect of smoking, PD and CAL in tooth-sites with baseline PD \geq 6mm will also be investigated with exploratory analyses using the following categories:

- Age (< median age; \geq median age)
- Gender (male, female)
- Current disease smoking status (smoker – has smoked within the past two years, non-smoker – has never smoked or quit > 2 years ago).

The model used for the original analyses of these variables will form the basis for separate analyses for each of these factors. However, in addition to the factors in the original model, an additional main effect (e.g. gender) and interaction term (e.g. gender by treatment) will be included in the model.

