2. PROTOCOL SUMMARY

Name of Sponsor/Company: Stemnion, Inc.
Name of Investigational Product: ST266 [Amnion-derived Cellular Cytokine Solution (ACCS)]
Title of Study: A randomized, double-blind, placebo-controlled study to evaluate the safety, efficacy, and treatment regimen of ST266 in subjects with moderate to severe periodontitis.
Study Center(s): Multi-center (6 clinical sites in the United States)
Phase of Development: Phase 2a
Objectives: Primary: To determine the efficacy of ST266 to reduce pocket depth (PD) adjunctive to scaling and root planing 270 days after initiation of treatment. Secondary: To determine safety and changes in: 
• Clinical attachment level (CAL)• Bleeding on probing (BOP)
Study Design: The study is a 9-month, randomized, double-blind, parallel-design study of subjects with existing moderate to severe periodontal disease randomly assigned to one of three groups. The primary endpoint of PD change will be evaluated following 270 days on study. Subjects will be followed for 9 months for safety and radiographic evaluations. Subjects who meet inclusion and exclusion criteria will be randomized to one of three treatment groups. Randomization will be stratified by site and smoker status (never smoked or quit smoking more than two years ago vs. has smoked within the last two years). Randomization will be blocked such that assignment to treatment groups both within sites and within smoker status will be approximately even (1:1:1). Treatment will be initiated after scaling and root planing (SRP). All subjects will be evaluated at baseline and Days 1, 15, 30, 60, 90, 180, and 270.
Number of Subjects (Planned): A total of 150 subjects will be enrolled in the study, 50 per group.
Study Duration per Subject: Each subject will be enrolled in the study for 9 months.
Diagnosis and main criteria for inclusion: Moderate to severe periodontal disease according to American Academy of Periodontists (AAP) definition (at least 6 teeth with 6mm or greater pocket depth and 3 mm or greater CAL at baseline). Inclusion Criteria: 
1. Provision of signed, written informed consent prior to participation in any study-related

procedures.

2. Good general health as evidenced by medical history.
3. Between 18 and 85 years of age at time of informed consent signature.
4. Male or female.
5. Minimum of 18 teeth, excluding third molars.

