2.6 Sample Size Determination

One hundred and fifty (150) subjects will be enrolled. The sample size for the study is based on the sample size required to compare treatment with ST266 versus placebo for the primary efficacy endpoint.

The number of subjects was estimated based on two meta-analysis studies that reviewed 50 and 72 articles respectively (Bonito, 2005).

Using the normal approximation for sample size determination for an independent sample t-test, and assuming a PD reduction of 0.5 mm on average (difference in means) with a standard deviation of 0.7 mm, $\alpha=0.05$ (0.025 per comparison, Bonferroni correction), and 85% power, a sample size of 44 per group will be required. The expected dropout rate is approximately 10% based on previous experiments; hence 50 subjects will be enrolled per group.

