6. DEMOGRAPHIC AND OTHER BASELINE CHARACTERISTICS

Baseline data (demography, medical history, dental history, and baseline disease characteristics) will be summarized.

Demography includes age, sex, race, and ethnicity. Sex, race, and ethnicity will be tabulated in frequencies and continuous summary statistics will be presented for age at screening. Data will also be presented in a listing.

The number and percentage of subjects with each medical history event will be presented by body system and event term. A listing will also be created which will include the body system, event term, whether the medical history event is ongoing and controlled, as well as the start and end dates of the event and any associated comments.

The number and percentage of subjects who have been diagnosed with periodontitis, abscesses, or who have had any oral surgeries or root canals, or are currently experiencing dental pain will be presented. A listing will also be created which will include the above events as well as their associated dates, the date the subject last visited a dentist or hygienist, frequency of flossing and mouth rinse, and interdental irrigation devices.

Results of the baseline oral exam will be listing by area examined and will denote an abnormal or normal result; and, if abnormal, the associated description of the abnormality will be listed. The presence of periodontal abscess or endodontic abscess will also be presented.

Tooth status at baseline will be presented in a listing by subject and tooth, and will denote whether the tooth is missing, sound, decayed, filled, fractured, has a crown, and/or is an implanted tooth.

Quadrants completed during the scaling the root planing procedure at visit 3 will be presented in a listing.

Demographic and baseline disease characteristics will be presented for the safety population.

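### SAP 8.4 splits age at the sample median before fitting the age-by-treatment interaction; if the effect changes roughly linearly with age, this gives up about 25% to 36% of the information on that change

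*SAP*

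**What the plan says.** SAP 8.4 (Examination of Subgroups) says that PD and CAL in tooth-sites with baseline PD of at least 6 mm "will also be investigated with exploratory analyses using the following categories". For age there are two categories, given as "Age (< median age" and its complement, at or above the median. The median is not given as a number, so the cut is fixed only once the sample is known. The other two factors, gender and smoking status, have two levels as the section defines them.

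For each factor the original model is kept, and "an additional main effect (e.g. gender) and interaction term (e.g. gender by treatment) will be included in the model".

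Age itself is recorded on a continuous scale. Eligibility in the SAP protocol summary (section 2) is "Between 18 and 85 years of age at time of informed consent signature", and SAP 6 states that "continuous summary statistics will be presented for age at screening". Neither document uses continuous age as an effect modifier, and neither gives a reason for the split.

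**The concern.** A median split treats all patients within a half as the same age and separates patients who lie just either side of the cut. When the treatment effect drifts steadily with age, the within-half variation carries information about that drift, and the split throws it away. The interaction is then estimated less precisely than the collected data allow. The result is also a contrast between two halves of this particular sample, which is hard to carry to a later trial with a different median.

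What is at stake is the width of an interval in an exploratory analysis. No planned claim is at risk. The trial was sized for the main effect, so precision on any interaction is already limited, and a further avoidable loss is worth removing if the cost is small.

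**Working it through.** **Inputs.** SAP 2.6 gives the effect and SD: "assuming a PD reduction of 0.5 mm on average (difference in means) with a standard deviation of 0.7 mm". It also gives "0.025 per comparison, Bonferroni correction), and 85% power, a sample size of 44 per group will be required". SAP 2.3 plans 50 per group. I use n = 50 per arm because SAP 8.1.1 imputes values for patients who withdraw, which keeps them in the ITT analysis. Assumed, because the documents do not give them: the age distribution (normal or uniform) and a treatment effect that is linear in age.

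**The plan's own figure.** n = 2 × [0.7 × (2.241 + 1.036) / 0.5]² = 42.1, so 43 per group against 44 stated. This reproduces closely enough to take SD 0.7 mm as the patient-level SD of PD change. The documents state no figure for the age interaction.

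**Median split.** The older-minus-younger difference in effect, for one active arm against placebo, is a contrast of four cells of 25 patients:

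SE = 0.7 × √(4/25) = 0.28 mm; 95% half-width = 1.96 × 0.28 = 0.55 mm.

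**Continuous age.** With age in SD units, the difference between arms in the slope on age has SE = 0.7 × √(2/50) = 0.14 mm per SD. To put this on the same older-minus-younger scale, multiply by k, the distance in SDs between the mean ages of the two halves. The information kept by the split is (k × 0.14 / 0.28)² = k²/4.

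| Age distribution | k | SE (mm) | 95% half-width (mm) | Information kept by split | Lost |
|---|---|---|---|---|---|
| Normal | 2√(2/π) = 1.596 | 0.223 | 0.44 | 2/π = 0.64 | 36% |
| Uniform | √3 = 1.732 | 0.242 | 0.48 | 0.75 | 25% |

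The split interval is therefore about 15% (0.28/0.242) to 25% (0.28/0.223) wider.

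**Sensitivity to the age distribution.** With one million draws per case, the loss was 31% to 35% for normal ages truncated to 18–85 (mean 40 or 50, SD 12 to 20). It was about 19% for a clearly bimodal example and about 42% for a right-skewed one. A simulation of the interaction model (50 v 50, normal age, SD 0.7, 4,000 runs) kept 61% of the information, close to the 64% from the formula.

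**Power, for illustration only.** For a 0.5 mm older-minus-younger difference with normal age and two-sided 0.05, the split gives z = 0.5/0.28 = 1.79 (43%) and continuous age gives z = 0.5/0.223 = 2.24 (61%). In a simulation of a three-arm patient-level model (6,000 replicates per setting), a 0.25 mm difference gave about 14% with the split and 18% with continuous age. With a true step of 0.5 mm exactly at the median, the order reversed: 37% with the split and 27% with continuous age.

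**Limits of the calculation.** It is a patient-level linear model. The planned model is a tooth-site GEE with baseline PD, site, smoking status and smoking-by-treatment terms (SAP 8.3.1). The widths in mm apply to PD; no SD for CAL is given. The proportional loss applies to both endpoints under the same assumptions.

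**The case against.** The strongest case is that this is a choice of display in an exploratory section. A median split gives balanced halves, needs no linearity assumption, is not driven by a few very young or very old patients, and puts age in the same format as gender and smoking. There is no bias, and simulated type I error is about 5% with either coding. All of this stands, and it is why the point is a minor improvement and not an error.

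Three stronger readings are tempting, and the documents do not support them.

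- A reader might infer that a fixed third of the information is lost. That needs both a bell-shaped age distribution and a linear change of effect. The documents give neither. Uniform ages give 25%, and a step at the median gives no loss.
- A reader might infer a large gain in power. Simulated gains of about 11 to 21 points appear only for older-minus-younger differences of 0.5 mm or more. A 0.5 mm difference equals the whole planned effect and means 0.25 mm benefit in one half and 0.75 mm in the other. At 0.25 mm the gain is 3 to 4 points, and both analyses have little power. SAP 8.4 also sets no alpha or decision rule for this interaction, and the notes to Table 8-1 limit p-values to treatment comparisons at Day 270. Precision is the appropriate measure.
- A reader might infer that efficacy conclusions are weakened. The analyses in SAP 8.3.1 and 8.3.2 do not use age at all.

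What survives the objection is the loss of precision under a roughly linear modification, together with the fact that a better analysis needs no new data.

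**Conclusion.** The point holds as a low-cost improvement to an exploratory analysis. Under a roughly linear change of effect with age, the split gives up about 25% (uniform age) to 36% (normal age) of the information. For PD this moves the 95% half-width from about 0.44–0.48 mm to about 0.55 mm, against a planned treatment effect of 0.5 mm. The figures rest on 50 per arm, SD 0.7 mm, a patient-level approximation to the planned GEE, and assumed age distributions. If the modification is a step at the median, the split is the better analysis. If the modification is small, neither coding will show it. Primary and secondary conclusions are unaffected.

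**What to change.** In SAP 8.4, enter age as a continuous covariate, centred, with its interaction with treatment, in the PD and CAL models. Report the change in treatment effect per 10 years and the estimated treatment difference at two or three pre-specified ages, each with a 95% CI. Keep the median split as a descriptive display beside it, to guard against a non-linear pattern. SAP 8.5 already treats PD in this order, with categories supplementing the continuous analysis.

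The cost is one sentence in SAP 8.4 and one change to the model code, with no new data. SAP 1 says the plan is being developed before database lock; made before then, the change is pre-specified, whereas the same analysis added outside the SAP would be labelled post hoc in the study report. The downside is that the continuous term assumes approximate linearity and is weaker than the split if the effect is really a step at the median.
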